- Acoustic assessment: The microphone is positioned at a 45° angle and at a standardized distance from the mouth of the participant. The participant is asked to sustain phonation on the vowels /a/ and /i/ at a comfortable loudness for 3-5 seconds and as low and as loud as possible, to glide to a high pitch and to a low pitch, and from a soft voice to a loud voice. They are asked to sustain the vowel /a/ for as long as possible. They are then asked to read the 6 CAPE-V sentences and to have a short natural conversation with the speech therapist. The participant is then asked to rate their perceived phonatory effort (PPE) on a scale.
- Self-Assessment questionnaire: the participant will be asked to fill out the Communicative
 Participation Item bank (CPIB) questionnaire, which consists of 10 questions on communication.

Participants will be stratified based on their muscle pressure measures: 1) within normal limits MIP and MEP; 2) preserved MIP and decreased MIP; 3) preserved MEP and decreased MIP; 4) decreased MIP and MEP. This stratification is crucial to the study design because it will ensure an equal repartition of the

different respiratory profiles and deficits across treatment groups. Participants that don't meet stratification requirements will be excluded from the study.

Participants will be blocked-randomized into three groups (allocation ratio 1:1:1): IMST, EMST and VFE (see description of the interventions below).

Experimental Interventions (Procedures to be performed solely as part of this research study):

Participants in all groups will attend four sessions with a study team member. Intervention sessions will last approximately 30-45 minutes each. Each session will include pre- and post-treatment muscle pressure and acoustic measurements.

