12.0 Data Management

Data Analysis Plan

Demographic characteristics will be compared across the 3 intervention groups, using a RxC contingency table method for categorical variables (gender, smoking history, voice use, racial and ethnic category) and a one-way ANOVA for continuous variables (age, weight, height). Baseline characteristics will be compared across the 3 intervention groups using a Kruskal-Wallis one-way analysis of variance by ranks for ordinal data (GFI, RSI, and VHI scores), a RxC contingency table for categorical variables (glottal gap shape, free edge contour, vertical level, phase closure) and a one-way ANOVA for continuous variables. Aim 1: To assess the effects of respiratory training on voice and respiratory outcomes in patients with presbyphonia. Data will be analyzed on an intention-to-treat basis using multifactor repeated measures generalized linear regression. Distributional assessment will be made for each outcome to confirm optimal distributional assignment and potential need for outcome transformation (i.e. log link). In the model, the repeated factor is time, which has two levels (pre- or post-intervention) and the independent factor is the intervention, which has three levels (IMST, EMST, VFE). In the case of a significant between-subjects effect, multiple comparison tests will be conducted to determine which groups differ. The post-hoc analysis will be done using Tukey's honestly significant difference (offering protection against type I error without being too conservative). Spearman and Person correlations will be calculated to establish inter and intrarater reliability. Aim 2: To identify profiles of presbyphonic patients that would benefit the most from respiratory training. Logistic regression will be conducted to predict which patients improved following inspiratory training and which patients improved following expiratory training, based on their baseline clinical characteristics. Two outcome variables will be indicative of meaningful clinical improvement: 1) MPT (to measure function), and 2) GFI (to measure patient perception of function). Meaningful clinical improvement will be defined by an increase of at least 4 seconds in MPT or a decrease of at least 4 points in GFI score. Participants will be dichotomized as having meaningful clinical improvement, or not, based on these outcomes. Predictors will include MIP, MEP, maximum SPL, breaths per minute, FVC, FEV1, and P_s. These measures were chosen because they are directly influenced by the integrity of the respiratory system.

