
Sample Size Justification

We considered maximum phonation time (MPT) as the primary outcome measure for sample size calculation. This measure was chosen because 1) low MPT is a hallmark of patients with presbyphonia, and 2) MPT is directly affected by both the laryngeal and respiratory systems. To estimate the expected effect size between VFE and the I+IVFE and E+VFE groups, we considered MPT values from groups of an

elderly population with different glottal closure and spirometry profiles (49). Considering that a combined intervention (inspiratory or expiratory training combined with voice therapy) would address both laryngeal and respiratory deficits, and that a voice therapy-only intervention would directly address only the laryngeal deficits, we compared MPT between the no-deficit group (complete glottal closure and normal spirometry) and the respiratory-deficit group (complete glottal closure and altered spirometry)(49). Based on these values and the pooled standard deviations, the expected difference between our control and experimental groups would represent a large effect size. As for the withinsubjects effect, a study by Nam et al.(50) found a 33% increase in MPT following a respiratory training intervention program in young adult singers. This corresponds to a very large within-subjects effect size with values of d exceeding 1.2. For Aim 2, we will assess improvement in 2 ways: function (a MPT increase of 4 seconds, which has been associated with a positive perceived effect following voice therapy in older adults(51)) and patient perception of function (a Glottal Function Index (GFI) score decrease of 4 points). An increase of 4 seconds in MPT and a decrease of 4 points on the GFI instrument both correspond to medium-large effect sizes considering the reported standard deviations of these measures in older subjects and in patients with glottal insufficiency (5.1 and 4.5, respectively) (42, 52). Based on the reported studies, the expected effect size for within-subjects and between-subjects differences was set at d=0.90. To have an 80% power to detect an effect size of d=0.90 with an alpha of 0.1 (since this is a pilot study), 15 participants are needed in each group. To account for loss to follow-up (estimated 10% dropouts rate), up to 16 participants will be recruited for each group, 48 patients total.

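### With three arms, Tukey's HSD after a significant overall test is valid but more conservative than needed, at a cost of about 2 to 16 points of power depending on the question

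*Combined protocol and SAP*

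**What the plan says.** Section 12.0 (Data Analysis Plan, Aim 1) describes a repeated-measures generalized linear regression with time at two levels, in which "the independent factor is the intervention, which has three levels (IMST, EMST, VFE". Section 10.0 allocates participants "into three groups (allocation ratio 1:1:1): IMST, EMST and VFE".

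Two layers of error control follow in consecutive sentences. The first is a gate: "In the case of a significant between-subjects effect, multiple comparison tests will be conducted to determine which groups differ". The second is the adjustment: "The post-hoc analysis will be done using Tukey's honestly significant difference (offering protection against type I error without being too conservative".

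The Sample Size Justification in the same section states "To have an 80% power to detect an effect size of d=0.90 with an alpha of 0.1 (since this is a pilot study", followed by "15 participants are needed in each group". It does not mention the Tukey step.

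**The concern.** The reason given for Tukey is that it protects without undue conservatism. Behind a gate, with three arms, it is conservative. Only two kinds of null configuration are possible:

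- All three means are equal. The gate itself then limits any false rejection to alpha.
- Exactly one pair is equal. Only one true null can be rejected, and a single unadjusted test limits that to alpha.

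The gate followed by unadjusted contrasts is therefore a closed test with strong familywise control. This argument fails with four or more arms.

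At stake is power for the contrasts that answer Aim 1. The trial is small and single-site, and sections 1.0 and 16.0 intend to read negative findings as evidence against respiratory training. Avoidable false negatives therefore have consequences.

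**Working it through.** **Inputs.** Three arms, 1:1:1 (sections 10.0 and 12.0). 15 evaluable per arm, d = 0.90, alpha 0.10 (section 12.0, Sample Size Justification).

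Assumptions:
- Tests are two-sided; the plan does not say.
- Alpha 0.10 applies to the analysis; it appears only in the sample-size text, so 0.05 was also run.
- The main pattern is VFE 0 and both trainings 0.9. The text says that "the expected difference between our control and experimental groups would represent a large effect size" but gives no three-mean pattern.
- Outcomes are normal with equal variance, and the gate and the contrasts test the same effect.

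**1. The plan's own figure.** Two-sample normal formula: n = 2 × ((1.645 + 0.842)/0.90)² = 15.27 per arm. Power at 15 is 79.4% by this approximation and 77.6% by the t test. The three-arm F test has noncentrality 15 × (2 × 0.81/3) = 8.1 and power 79.8%. The stated 15 is reproduced within rounding. One-sided alpha 0.10 would need only 12, so two-sided is the better-fitting reading.

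**2. The extra hurdle.** Error df = 3 × 15 − 3 = 42. Critical |t| is 1.682 unadjusted and 2.110 for Tukey (q/√2). The standard error of a difference is √(2/15) = 0.365 SD. The observed difference needed is 1.682 × 0.365 = 0.61 SD unadjusted, against 2.110 × 0.365 = 0.77 SD with Tukey.

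**3. Familywise error** (simulation, 400,000 trials per scenario, alpha 0.10):

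| Procedure | All means equal | Two equal, third far away |
|---|---|---|
| Gate + unadjusted | 10.0% | 10.0% |
| Gate + Tukey | 9.2% | 4.1% |
| Tukey, no gate | 10.0% | 4.1% |
| Unadjusted, no gate | 22.4% | 10.0% |

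The gate with unadjusted contrasts holds 10%, and so does Tukey alone. Stacking the gate and Tukey only pushes the error below 10%.

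**4. Power after the gate** (15 per arm, alpha 0.10; means in the order VFE, training, other training):

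| Target | Unadjusted | Tukey | Loss (points) |
|---|---|---|---|
| One named training vs VFE, both work (0, 0.9, 0.9) | 72.5% | 63.6% | 9 |
| One named training vs VFE, only that one works (0, 0.9, 0) | 72.4% | 63.5% | 9 |
| d = 0.90 contrast, third arm midway (0, 0.9, 0.45) | 67.0% | 63.0% | 4 |
| Both trainings vs VFE (0, 0.9, 0.9) | 65.2% | 48.9% | 16 |
| At least one training vs VFE (0, 0.9, 0.9) | 79.8% | 78.3% | 1.6 |

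**5. Sensitivity, first row.**
- n = 14: 69.3% vs 60.3%.
- n = 16: 75.4% vs 66.7%.
- Alpha 0.05, n = 15: 60.3% vs 51.3%.

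**6. In patients.** Gate plus Tukey needs about 18 evaluable per arm to match gate plus unadjusted at 15 for one named contrast (3 × 3 = 9 more patients), and about 20 for both contrasts (3 × 5 = 15 more).

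**7. Which layer to drop.** Keeping Tukey and dropping the gate gives 64.0% for the named contrast, a gain of about half a point. Tukey is the layer that costs power.

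**The case against.** **The plan is not wrong.** A gate followed by Tukey controls type I error, and choosing it over gated unadjusted tests is a choice between valid procedures. This stands. A reader might infer that the analysis is in error; the documents do not support that.

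**Tukey does protect.** A reader might infer that the second layer buys nothing. It lowers the actual error for a true null pair from 10% to about 4% when the third arm differs. What it does not do is supply protection needed to hold the nominal level within one outcome. The distinction matters because section 4.0 lists many outcomes and the plan states no adjustment across them. Neither method repairs that, but dropping Tukey does allow more false positives per outcome.

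**Nine points is one target among several.** The Aim 1 hypotheses in section 1.0 are worded as inspiratory and/or expiratory training. If both trainings work and success means showing at least one of them, the loss is under 2 points. This stands, and the result should be read as a range. If only one training works, the named-contrast loss is again about 9 points.

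**The figures presume a gate that the plan does not clearly state.** Section 12.0 gates on a between-subjects effect in a pre/post model. Read literally, as the arm effect averaged over both times, that gate passes only about 36 to 40% of the time (post-treatment d = 0.90, assumed pre-post correlation 0.5 to 0.7). The Tukey loss for one contrast is then about 3 to 6 points. This stands: the gains quoted require gate and contrasts to address the same effect, so the fix must define the gate. A mismatch would also break the closed-test argument. If true baseline means differed between arms, gated unadjusted tests of change could reach about 22% familywise error. Randomisation rules out true baseline differences, but the plan should not depend on that.

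**Intervals and distributions.** Tukey offers simultaneous intervals. Three unadjusted 90% intervals jointly miss about 22% of the time. The plan mentions no intervals, but the loss should be disclosed. Exact control holds for the normal equal-variance model; section 12.0 also allows outcome-specific distributions and a log link, where control is approximate.

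**Conclusion.** The point holds as an efficiency improvement to a valid plan. Within one outcome and with exactly three arms, the gate plus unadjusted contrasts keeps the same nominal familywise error and rejects whenever gate plus Tukey does. At the plan's own inputs the gain is about 9 points for one named training-versus-VFE contrast, about 16 for showing both, about 4 for the d = 0.90 contrast with the third arm midway, and under 2 for showing at least one when both work. The 9-point figure is stable over n = 14 to 16 and alpha 0.05 to 0.10.

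The conclusion rests on two-sided testing, d = 0.90 on the analysed scale, approximate normality with equal variances, and a gate on the same effect as the contrasts. It does not show that the planned analysis is invalid or that Tukey has no effect on error.

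**What to change.** In section 12.0, Data Analysis Plan, Aim 1, replace the gate and Tukey sentences with text to this effect: the overall test is the 2-df test of the arm effect on improvement (arm-by-time, or the baseline-adjusted arm effect) at the trial's alpha; if it is significant, the three pairwise contrasts of that same effect, from the same model, are tested without adjustment at the same alpha, as a closed test for three arms. State alpha and sidedness there, and add that an adjusted procedure applies if an arm is ever added.

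The cost is a short edit and no extra patients. The plan should also acknowledge:

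- The actual error for a true null pair rises from about 4% to the nominal 10% when the third arm differs.
- The matching confidence intervals are not simultaneous. Label them so, or report Tukey intervals alongside.
- Error control is approximate for non-normal or log-link outcomes.
- Multiplicity across the Aim 1 outcomes is not addressed by either method and needs its own statement.

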Specific Aim 1: To measure the effects of respiratory training on respiratory and voice outcomes in patients with presbyphonia. Hypothesis 1: The respiratory training groups (inspiratory and/or expiratory) will demonstrate greater improvement in respiratory outcomes, measured through pulmonary function tests and respiratory pressure measures, compared with the voice exercises-only group. Hypothesis 2: The respiratory training groups (inspiratory and/or expiratory) will demonstrate greater improvement in voice-related outcomes than the voice exercises-only group.

Secondary Aim 1: To assess the reliability of the ratings for subjective outcomes (videostroboscopy ratings and perceptual judgements of voice quality). Hypothesis 1: Intra-judge reliability will be of at least 80%. Hypothesis 2: Inter-judge reliability will be of at least 70%.

Specific Aim 2: To determine how baseline measures of respiratory function influence the effects of respiratory training (respiratory and voice outcomes). Hypothesis 1: inspiratory training will have maximal effect on patients with decreased maximum inspiratory pressure (MIP). Hypothesis 2: Expiratory will have maximal effect on patients with decreased maximum expiratory pressure (MEP).

This is an initial feasibility and mechanistic study that has the potential to reveal that respiratory training can significantly improve outcomes from voice therapy by acting in synergy with voice exercises. Currently,

much time is spent in voice therapy on subthreshold 'breathing exercises' that lack evidence. This project will provide guidance for evidence-based and theory driven approaches to leverage respiratory function to improve voice therapy. Conversely, negative findings from this study would indicate that respiratory function is ineffective and not a viable target for therapy in this patient population.

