6.0 Number of Subjects

Forty-eight patients-participants and up to six raters-participants will be recruited for the study.

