10.0 Study Design / Methods

Overview

After being enrolled in the study, treatment-seeking patients with a diagnosis of presbyphonia will undergo baseline respiratory assessments including spirometry and respiratory muscle strength measures as well as voice recordings (acoustic assessments). Participants will then be blocked-randomized (based on their MIP and MEP) to one of three groups using a 3-parallel arm design: (2 experimental groups and 1 control group), using a 3-parallel arm design: 1) inspiratory training (IMST) (experimental group), 2) expiratory training (EMST) (experimental group), or 3) standard of care (VFE) (control group), delivered four times (see table 1 for participant timeline). The sessions will occur on the same days as the participants' scheduled voice therapy sessions when possible. Participants will be asked to practice their respective exercises for 10 minutes, twice daily, seven days a week during the duration of the study. A final assessment session, after the 4th therapy session, will mirror the baseline measures. Participants will receive a monetary compensation of \$20 for each study visit, for a maximum of \$80 for the whole study. Payments will be made via cash. Outcomes that rely on subjective judgment (visual ratings of

videostroboscopy and perceptual judgments of voice quality) will be rated by trained judges (SLPs) blinded to the group assignment. [**Note**: Long-term follow-up will not be conducted. This study's focus is on the mechanistic effects of the intervention; future studies, given positive outcomes from this study, will explore the effectiveness and long-term effects.]

Table 1: Participant Timeline

Visit 1	Visit 2	Visit 3	Visit 4
Baseline assessment session			
Therapy session 1	Therapy session 2	Therapy session 3	Therapy session 4
			Final assessment session

Patient Participants

Standard of Care Assessments (Procedures being performed already for diagnostic purposes)

- Laryngeal imaging: prior to the examination, the laryngologist will administer topical lidocaine and neosynepherine in a spray to one of the nasal cavities. The laryngologist then passes the camera through the nose to examine the vocal folds. The participant will be asked to sustain phonation on the vowel /i/ for at least 3 seconds and to repeat with pitch and loudness variations.

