Unknown risks: Respiratory training has never been tested on patients with presbyphonia. The results of this combination are unknown. Although unlikely, there is a slight risk that unforeseen adverse events could result from this combination.

Protections Against Risk

Loss of confidentiality: Protection against the loss of confidentiality will be diminished by 1) completing study aims at one data collection site, 2) minimizing the participants involved to only those needed to accomplish the study aims (see sample size justification above), 3) de-identifying data at the earliest opportunity, and 4) maintaining stored data in locked/password protected locations whose access is restricted to members of the study team. All data collection and study activities will be conducted at MUSC. The patient subject sample will include up to 48 patients referred for a videostroboscopy within the scope of their usual care at MUSC and who meet the inclusion criteria. The sample will be limited to the MUSC site because historical accruals have been shown sufficient to meet power (see participant section above). Six participant raters will be recruited from SLPs who have experience with voice disorders. An alphanumeric identifier will be used instead of patient participant name and rater participant name at the earliest possibility. In order to ensure participant's confidentiality, database entry will be password protected and study documents will be maintained in a locked cabinet in the PIs locked office. Patient identity will also be protected by confidentiality policies and procedures already in place at the MUSC site. A participant may withdraw from the study at any time without penalty or prejudice.

Spirometry and muscle pressure testing: If the patient-participant manifests signs of discomfort or dizziness, the spirometry or muscle pressure testing maneuver will be interrupted following the American Thoracic Society's (ATS) recommendations(47). Stopping the maneuver will avoid a syncope, which could follow due to the interruption of venous return to the thorax during prolonged exhalation. As a precaution, all assessments will be done in a sitting position, in a chair with arms and without wheels to prevent falls.

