16.0 Potential Benefits to Subjects or Others

The experimental groups may benefit from receiving a respiratory training intervention. Respiratory training directly targets the respiratory system and *could* lead to greater improvements in both respiratory and voice outcomes than those observed with voice therapy alone.

There is a possibility that the participant will not directly benefit from being part of this research project.

For the subjects of the study, as well as for future voice patients who could benefit from this intervention if it were to be proven effective and to be implemented in common usual care, it could lead to important benefits:

- Improved respiratory and voice outcomes;
- Greater improvements in a person's daily activities involving communication;
- Reduced number of voice therapy sessions needed
- Improved voice-related quality of life

Because communication is a social activity, these benefits are also susceptible to impact the quality of life of the participants' significant other, family and caregiver.

The minimal risks associated with this research project are reasonable in relation to the potential benefits to the study participants and others. In the case where the intervention is not shown to be more efficacious than voice therapy only, the subjects would still receive the benefits from standard of care voice therapy.

Participant-raters will be compensated at a rate of \$40 for every 10-rating package (one package includes an endoscopy recording and an audio file). It is estimated that each rater will rate a total of 39 packages, for a total of \$160 for their participation in the study.

Both patient participants and participant raters may indirectly benefit, along with other patients, clinicians and society from the dissemination and implementation of the results of this research. The results of this research if in-line with our pilot data, will provide evidence that will serve as a guide for speech-language pathologists to inform patient management decisions. In general, any study that improves the effectiveness of voice intervention and the evidence upon which treatment recommendations are based may improve the health status and quality of life of patients and decrease the economic burden of voice disorders. These benefits outweigh the minimal risks that may result from loss of confidentiality and discomforts associated with the respiratory training interventions.

Importance of the Knowledge to be Gained

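### The 80% and 70% rater-reliability targets have no named statistic, and the only planned method, correlation, cannot detect systematic disagreement within a rater pair

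*Combined protocol and SAP*

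**What the plan says.** Section 1.0 of the combined protocol and SAP makes rater reliability an aim in its own right: "To assess the reliability of the ratings for subjective outcomes (videostroboscopy ratings and perceptual judgements of voice quality"). It attaches two hypotheses with thresholds: "Intra-judge reliability will be of at least 80" per cent, and "Inter-judge reliability will be of at least 70" per cent. Neither says what is being measured.

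The Data Analysis Plan in section 12.0 has a single sentence on the subject: "Spearman and Person correlations will be calculated to establish inter and intrarater reliability" (I read the second name as Pearson). It does not tie either coefficient to the targets, assign coefficients to CAPE-V or VALI items, or say how results from several raters are combined. ICC, kappa and percent agreement appear nowhere.

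On the rating design, section 10.0 (Rater Participants) has raters score each participant's pre- and post-intervention recordings, plus a further 20% sample for intra-rater testing. Section 16.0 gives the load: "It is estimated that each rater will rate a total of 39 packages". Section 15.0 says "Six participant raters will be recruited from SLPs who have experience with voice disorders", while section 6.0 says "up to six raters-participants will be recruited for the study". No section states how many raters score each recording.

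**The concern.** A hypothesis with a numerical threshold needs a defined statistic. The 80% and 70% could mean a correlation, percent agreement or an ICC, and each can give a different verdict on the same ratings.

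If the only planned method is applied, a second problem follows. Pearson and Spearman measure whether two raters order and space the recordings alike, not whether they give the same scores. If one judge scores every voice 15 units more severe than another, their correlation is what it would be with no difference. The inter-judge hypothesis could then be reported as met when raters systematically disagree, and readers would take the CAPE-V and VALI ratings as more interchangeable between judges than they are.

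**Working it through.** The targets are not derived from anything in the documents, so there is no plan figure to reproduce. The check is how far correlation and agreement can part.

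**Inputs.** Targets of 0.70 and 0.80 (section 1.0); 48 participants with pre and post recordings, so 96 recordings, and a 20% repeat sample (sections 6.0 and 10.0); 39 packages per rater (section 16.0). The SDs and offsets below are assumptions, in units of a continuous rating scale.

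**1. Correlation against agreement, offset b.** With recording SD 20 and error SD 8, the variances are 400 and 64.
- Pairwise Pearson = 400/(400 + 64) = 0.862, whatever b is.
- Absolute-agreement single-rating ICC = 400/(464 + V), where V is the variance of the rater offsets (n − 1 divisor).
- ICC = 0.70 when V = 400/0.70 − 464 = 107.43.
- Two raters: V = b²/2, so b = √214.86 = 14.7.
- Three of six raters high by b: V = 0.3b², so b = 18.9.
- One of six high by b: V = b²/6, so b = 25.4.

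**2. Sensitivity to the assumed SDs (two raters).**

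| Recording SD / error SD | Pearson | V at ICC 0.70 | b |
|---|---|---|---|
| 25 / 6 | 625/661 = 0.95 | 892.86 − 661 = 231.86 | 21.5 |
| 20 / 8 | 0.86 | 107.43 | 14.7 |
| 15 / 9.5 | 225/315.25 = 0.71 | 321.43 − 315.25 = 6.18 | 3.5 |

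As Pearson falls to 0.70 the offset needed goes to zero.

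**3. Rescaling.** If the second rater's scores are compressed by a factor k about the same mean, Pearson stays at 0.862 and agreement is 800k/(464(1 + k²)). At k = 0.5 this is 400/580 = 0.69; at k = 0.52 it is 0.71. Under these SDs only a near halving of the range changes the verdict.

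**4. Rating load.** 96 × 1.2 = 115.2 packages would be needed from a rater who scored everything, so at 39 no rater does. Two designs fit 39 equally well:
- six raters, two ratings per recording: 115.2 × 2/6 = 38.4;
- three raters, one rating per recording: 115.2/3 = 38.4.

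In the second design no inter-rater statistic can be estimated, correlation included.

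**5. Intra-rater pairs must not simply be stacked over raters.** With three of six raters 20 units high, the offset variance (n divisor) is 100. In a stack of first and repeat ratings it counts as between-pair variance and raises the ICC. With error SD 11, 400/521 = 0.77 becomes 500/621 = 0.81 and crosses the 0.80 target. With error SD 8, 0.86 becomes 500/564 = 0.89.

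**6. Precision of the intra-rater estimate.** 20% of 96 is about 19 recordings. Around 0.80, the Fisher-z 95% interval is 0.54 to 0.92 for 19 independent pairs and 0.65 to 0.89 for 38. If two raters each repeat the same 19 recordings, the 38 pairs are not independent, and the narrower interval overstates precision.

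**7. Weights for ordinal items.** In a four-level example with 96 items, uniform margins and 48 one-step disagreements, linear weighted kappa is 1 − 0.5/1.25 = 0.60 and quadratic is 1 − 0.5/2.5 = 0.80. The choice of weights alone can decide a 0.70 verdict.

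**The case against.** The strongest case is that little depends on this. The Aim 1 model compares pre with post, and a constant rater offset cancels from that change if the same raters score both recordings, as section 10.0 can be read. For that use, consistency is a defensible property. The raters are experienced and trained (section 10.0: "perceptual judgments of voice quality) will be rated by trained judges (SLPs"), so offsets may be small. MPT and GFI do not depend on judges, and this is a secondary aim of a pilot study.

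Much of this stands and sets the severity. It does not remove the point: cancellation concerns change scores, whereas Secondary Aim 1 is a hypothesis about agreement between judges, and section 12.0 gives it no other analysis. Nor can one say that only large offsets matter, since that holds only when the correlation is well above 0.70.

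A reader might infer more than the documents support:
- That correlations will be run on unordered categories, where the result would depend on arbitrary codes. Section 12.0 lists glottal gap shape, free edge contour, vertical level and phase closure as categorical for the baseline comparison; it does not say that correlations will be applied to them.
- That each recording is certainly scored by two raters. The load fits one rating by three raters equally well.
- That the percentages are meant as correlations. This is likely, because no other method is planned, but it is not stated.

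**Conclusion.** The point holds and is minor. The two reliability hypotheses have no defined statistic, and the only planned method cannot detect a constant offset or a rescaling within a rater pair. The invariance is mathematical and needs no data. How large an offset would reverse the inter-judge verdict does depend on assumptions: 14.7 units for two raters at SDs 20 and 8, from 3.5 to 21.5 over the SD pairs tabulated, and near zero when Pearson is close to 0.70. The documents contain no rater data with which to narrow this.

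The consequence is confined to the Secondary Aim 1 conclusion and to how the CAPE-V and VALI ratings are interpreted. Nothing here bears on the sample size or on the MPT and GFI results.

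**What to change.** In section 12.0, replace the reliability sentence with:

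> Inter-rater reliability of continuous ratings will be estimated by an absolute-agreement single-rating ICC from a mixed model with recording and rater as random effects, with rater variance in the denominator only. Ordinal items will use a multi-rater weighted agreement coefficient that allows each recording to be scored by only some raters, with the weights fixed before rating begins. Any unordered items will use multi-rater unweighted kappa, with percent agreement shown beside it. Intra-rater reliability will compare first and repeat ratings of the same recording by the same rater with an absolute-agreement ICC or kappa, estimated within rater and combined across raters (or from a model with a rater term kept out of the numerator), so that differences between raters do not raise it. All estimates will have 95% CIs that allow for the same recording being repeated by more than one rater. The 0.70 and 0.80 targets refer to these statistics.

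In section 10.0 (Rater Participants), state how many raters score each recording and that the same raters score a participant's pre and post recordings. Reconcile the number of raters in sections 6.0 and 15.0 with the 39 packages in section 16.0.

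**Cost.** One paragraph and one line of text. With six raters at 39 packages each, 6 × 39/115.2 = 2.03 ratings per recording are already planned, so none need be added. With three raters the figure is 1.02, and more ratings would be needed for any inter-rater estimate. The downside is that reported reliability may be lower than with correlation, which makes the targets harder to meet.
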